The HD grid catheter is still a traditional "point by point" mapping system whereby small areas of the atrium are examined in sequence. Non-contact dipole density mapping facilitated by the AcQMap system from Acutus Medical allows real-time visualisation of whole chamber activation during AF and reveals complex propagation patterns. These patterns are highly variable between patients and their detailed analysis may identify important patterns related to the underlying electrophysiological substrate that may further our understanding of AF mechanisms and help guide effective ablation strategies.

This study therefore aims to conduct detailed EAVM using the Abbott HD grid catheter in 5 control patients undergoing ablation of left sided accessory pathways who are thought to have normal atria in order to define normal voltage amplitude and the response to changing activation rate. Detailed EAVM will then be performed in patients undergoing catheter ablation for AF in order to evaluate atrial properties at both long and short pacing cycle lengths. In 2 separate subgroups, the orthogonal HD grid mapping will be compared to either AcQMap propagation patterns or to a conventional bipolar ablation catheter with contact force. It is hypothesised that regions of intermediate voltage will demonstrate exaggerated slowing in conduction velocity and broadening of electrograms with shortening cycle length compared to regions of preserved amplitude, which will correlate with regions of slow and irregular propagation patterns during atrial fibrillation and late gadolinium enhancement on cardiac MRI. Furthermore, EAVM using the HD grid catheter will reveal higher mean electrogram amplitude compared to bipolar mapping with a lower surface area identified as low voltage (<0.5mV). The improved mapping resolution provided by the HD wave solution and HD grid catheter alongside use of varying activation times will facilitate greater understanding of the variable and patient specific AF substrate involved in AF maintenance. It is anticipated that combining this with non-invasive assessment of fibrosis distribution through cardiac MRI and AF propagation patterns visualised by panoramic mapping will provide pilot data with the potential to identify sub-groups of AF phenotypes. This data can then be applied to larger multi-centre studies of substrate mapping to better characterise the arrhythmic substrate and develop patient specific ablation strategies.

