5. STUDY DESIGN

This is a prospective non-randomised mechanistic study of 35 patients including a control group of 5 patients with SVT and 30 patients undergoing elective AF ablation.

The 30 patients undergoing AF ablation will include 10 who are undergoing elective AcQMap guided procedures in order to correlate non-contact propagation patterns with contact substrate mapping. These 10 patients will also undergo cardiac MRI before and after the ablation procedure.

The remaining 20 patients will also undergo electroanatomical voltage mapping using a contact force guided bipolar ablation catheter in order to compare the two methods/technologies. This is a non-blinded comparison study.

The 5 control patients will be undergoing elective catheter ablation procedures for left sided accessory pathways. Additional left atrial electroanatomical mapping will be performed to define normal electrophysiological properties for comparison.

Participants will be identified in clinic or after listing for the procedure. Screening and formal recruitment will then be undertaken, with the research study conducted during the ablation procedure. No follow up is required but participants undergoing AcQmap guided ablation and cardiac MRI will undergo a repeat cardiac MRI within 6 months following the procedure.

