7.7. Study visit (excluding control group)

As part of standard care, a 12 lead ECG will be performed for all patients following arrival on the day of their procedure. In line with standard practice in this institution all procedures will be undertaken under general anaesthesia.

Venous access, trans-septal puncture and placement of standard electrophysiology catheters will be undertaken as per standard clinical care. Anticoagulation will be administered following trans-septal puncture in line with standard protocols.

Please see appendix A for detailed study flow chart.

All patients

All study patients will undergo electroanatomical voltage mapping (EAVM) using the Abbott Advisor HD Grid (SE) mapping catheter using the orthogonal wave setting (HD wave solution) in the same manner as described above. If in AF at the start of the procedure direct current cardioversion (DCCV) will be used to restore sinus rhythm. This can be repeated at the discretion of the operator if initially unsuccessful (including internal cardioversion if necessary). If unsuccessful then the patient will no longer be included in the study and the procedure should continue according to standard clinical care.

Mapping will then be undertaken during bipolar pacing from the mid point of the coronary sinus catheter at a cycle length of 800ms for 4 beats followed by a single extrastimulus with coupling interval of 300ms (or the shortest captured cycle length if longer). Atrial geometry can be acquired concurrently. Care must be taken to keep the catheter in each position to record all 5 cycles before moving to acquire new points aiming for a minimum of 300 points in total with full and equal covering of the atrial surface. Interpolation threshold should be set to 7mm with points filtered to within 5mm of the surface anatomy (interior and exterior projection). Initial map collection should be specified as a CFAE map set to collect points with the catheter stationary for 5 seconds. Subsequent analyses offline will use the Precision turbomap feature to adjust the data displayed. Ablation and the rest of the procedure can then be performed according to standard clinical practice.

Post procedure care including subsequent discharge will continue in line with standard clinical practice.

Subgroup undergoing contact force guided mapping

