20 patients undergoing AF ablation will have a further map completed using a contact force guided bipolar irrigated ablation catheter (Abbott Tacticath) during the same pacing protocol. For all voltage maps a minimum of 300 points should be obtained with full and equal covering of the atrial surface, interpolation should be set to 7mm, and set to only include points with contact force between 5 and 50grams.

Subgroup undergoing AcQMap guided mapping and ablation

10 patients with persistent AF who are undergoing AcQMap guided elective catheter ablation procedures will be included in this sub-study. All patients will undergo the same main study mapping procedure outlined above. In addition, AcQMap recordings will also be obtained. Recordings will be made during pacing with the same main study protocol and two 30 second recordings will be undertaken during AF. HD grid contact recordings will then also be obtained in regions of prominent rotational and irregular conduction identified by AcQMap and ablation performed at the operator's discretion.

For patients presenting in sinus rhythm or AF, all required mapping should be completed in the presenting rhythm followed by either AF induction (using incremental burst atrial pacing) or DCCV respectively before completion of mapping procedures. Ablation in line with standard clinical care will be undertaken following completion of all mapping procedures.

For an outline of study procedures versus standard care and estimated time requirements, please see appendix B.

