7.9. Discontinuation/Withdrawal of Participants from Study

Each participant has the right to withdraw from the trial at any time. In addition, the Investigator may discontinue a participant from the trial at any time if the Investigator considers it necessary for any reason including:

- Pregnancy
- Ineligibility (either arising during the trial or retrospectively having been overlooked at screening)
- Significant protocol deviation
- An adverse event which requires discontinuation of the catheter ablation or results in inability to continue to comply with trial procedures
- Withdrawal of Consent

If a patient is withdrawn or voluntarily withdraws from the trial prior to the study procedure then all study data collected will be excluded and they will be replaced in the study. If any event during the procedure results in necessary deviation from the study protocol on grounds of clinical necessity then any data collected up to that point will be analysed. It may be required to recruit additional patients if this occurs depending on the extent to which data had been collected. This is at the discretion of the chief investigator.

The reason for withdrawal will be recorded in the CRF.

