9. STATISTICS AND ANALYSIS

9.1. Description of Statistical Methods

This is a mechanistic study exploring a change in electrogram morphology. This will be expressed as a proportion of signals recorded within each amplitude bracket. Statistical comparisons using the chi-square tests of 2 proportions will be made to look for significant differences at long and short cycle length.

In the sub-study comparing voltage mapping methods, simple statistical analysis will be used to compare voltage amplitudes obtained by each method in sinus rhythm and in AF. Means will be compared using independent sample t-test.

Retrospective analyses may be conducted to explore trends in electrophysiological mechanisms identified and their relation to demographic, anatomical, or clinical features recorded and in line with secondary outcome measures.

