For all maps obtained in this subgroup using both the HD grid and ablation catheter, bipolar voltage amplitudes will be compared. Mean amplitudes will be compared for the entire chamber and each atrial segment (anterior, septal, inferior wall, posterior wall, roof, lateral wall). Each sampling point obtained using the ablation catheter in sinus rhythm/baseline pacing cycle length will then be compared to an equivalent nearest point obtained by the HD grid in sinus rhythm/baseline pacing cycle length to give a difference (+/-) in amplitude recorded. Mean differences will be compared for the whole atrium and each segment as outlined above.

The outcome measures will be assessed in all patients in whom the study procedure was performed.

AcQMap subgroup:

Qualitative and quantitative assessments of conduction patterns identified on AcQMap during AF will be made with regions of frequent focal firing, slow conduction, rotational activation or irregular activation identified (according to AcQTrack and visual interpretation of the operator in line with and according to

their prior experience). Contact electrograms using the HD grid will be recorded at these regions and classified according to their degree of fractionation. Regions identified as above by the operator will be compared to the rest of the atria according to sinus rhythm voltage amplitude and proportional change in electrogram morphology and conduction velocity with changing pacing cycle length.

The outcome measures will be assessed in all patients in whom the study procedure was performed.

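### The catheter comparison is given an unpaired t-test with no stated unit of analysis, although the same 20 patients are mapped with both catheters

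*Combined protocol and SAP*

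**What the plan says.** Section 5 sets up the sub-study: "The remaining 20 patients will also undergo electroanatomical voltage mapping using a contact force guided bipolar ablation catheter". These 20 also have the HD grid map, because section 7.7 states "All study patients will undergo electroanatomical voltage mapping (EAVM) using the Abbott Advisor HD Grid (SE) mapping catheter". The same section has the further map made with an "irrigated ablation catheter (Abbott Tacticath) during the same pacing protocol", and asks for at least 300 points per voltage map.

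Section 9.1 gives the analysis of this comparison in one sentence: "Means will be compared using independent sample t-test". It does not say whether a mean is taken over patients, segments or individual points. The only other test in the document is a chi-square test, for electrogram morphology at long and short cycle length.

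Section 9.3 describes the quantities. For the means: "Mean amplitudes will be compared for the entire chamber and each atrial segment". For the points, each ablation-catheter point "will then be compared to an equivalent nearest point obtained by the HD grid", which gives a signed difference to be averaged over the atrium and by segment. No test is named for either quantity, and neither is first summarised within a patient.

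**The concern.** An independent-sample t-test assumes that the two sets of values are unrelated and that the values within each set are independent of one another. Neither assumption fits this design. A patient with generally high voltage will tend to show it on both maps, and the points of one map share a patient, a catheter and a session.

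Section 3 makes a directional prediction: "EAVM using the HD grid catheter will reveal higher mean electrogram amplitude compared to bipolar mapping". The comparison of means is where that prediction is tested. With the unit left open, the same data can give opposite answers. Patient means may hide a difference that pairing would show, and pooled points may declare a difference that is only variation between patients. Settling the unit after the data are seen would leave the result open to that choice.

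**Working it through.** The plan gives no SD, correlation, effect size or power for this comparison, so there is no figure of its own to reproduce.

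**Inputs from the protocol:** n = 20 patients with both maps; m = 300 points per map (the stated minimum), hence 20 × 300 = 6,000 points per catheter.

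**Assumed inputs:** point SD 1.0 mV; points independent within a patient; true difference 0.15 mV; two-sided 5% level; between-patient SD (sb) 0.1 to 0.5 mV; SD of the patient-level catheter difference (sd) 0.1 to 0.5 mV.

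**Model:** patient map mean = shared patient effect (variance sb²) + patient-by-catheter effect (variance sd²/2 per catheter) + point error (1/300).

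**Patient means as the unit**

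- SE used by the independent test = √[2(sb² + sd²/2 + 1/300)/20]
- True (paired) SE = √[(sd² + 2/300)/20]
- Correlation of the two maps = sb²/(sb² + sd²/2 + 1/300)

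At sb = 0.2 and sd = 0.2:

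- independent SE = √[2(0.04 + 0.02 + 0.0033)/20] = 0.080
- paired SE = √[(0.04 + 0.0067)/20] = 0.048
- correlation = 0.04/0.0633 = 0.63

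Simulated power (200,000 trials per cell):

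| Test | sd 0.1 | sd 0.2 | sd 0.3 | sd 0.5 |
|---|---|---|---|---|
| Independent, sb 0.1 | 98.1% | 75.1% | 48.0% | 22.8% |
| Independent, sb 0.2 | 62.0% | 42.9% | 29.9% | 17.4% |
| Independent, sb 0.3 | 12.6% | 13.6% | 13.0% | 10.9% |
| Independent, sb 0.5 | 0.1% | 0.4% | 1.1% | 2.7% |
| Paired, any sb | 99.8% | 83.8% | 53.5% | 24.2% |

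With no true difference, the independent test rejects in under 0.1% to 4.3% of trials, against 5% for the paired test. At sb = 0.1 and sd = 0.5 the correlation is only 0.07 and the loss is negligible.

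A second calculation, by correlation and with an assumed difference of 0.5 SD, shows the same pattern. Power is 33%, 30% and 25% unpaired against 43%, 56% and 78% paired, at correlations 0.3, 0.5 and 0.7.

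**Pooled points as the unit**

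- SE used = √[2(1 + sb² + sd²/2)/6000]
- True SE = √[(sd² + 2/300)/20]
- Type I error = 2[1 − Φ(1.96 × SE used/true SE)]

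At sb = 0.1 and sd = 0.1 the SE used is 0.0184 and the true SE 0.0289. The ratio is 0.637, so the error is 2[1 − Φ(1.25)] = 21%.

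| sb | sd 0 | sd 0.1 | sd 0.2 | sd 0.3 | sd 0.5 |
|---|---|---|---|---|---|
| 0.1 | 4.9% | 21.2% | 45.2% | 59.7% | 73.6% |
| 0.5 | 2.8% | 16.5% | 40.4% | 55.8% | 71.1% |

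Point-level simulation (4,000 trials per cell) agrees to within about one percentage point.

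**Sensitivity to independence of points.** Suppose correlation specific to each map reduces 300 points to an assumed 100 effective points. With sd = 0 the true variance is then (2/100)/20 = 0.001, and the variance used is 2(1 + sb²)/6000. The ratio of true to used is 3/(1 + sb²), which is 2.97 at sb = 0.1 and 2.40 at sb = 0.5. Type I error is about 26% and 21%, with no variation at all in the catheter difference. Correlation shared by both catheters, from mapping the same tissue, moves the error the other way.

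**The case against.** The strongest reply is that pairing is already in the plan. Section 9.3 matches each ablation-catheter point to its nearest HD grid point and averages the signed differences, so the within-patient effect will be estimated. That is correct, and a reader who inferred that the plan overlooks pairing would be wrong. What is missing is valid inference: no test is attached to those differences, they are not summarised within a patient, and the one test named is for unpaired data.

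A second reply is that the comparison is secondary, has 20 patients, and sits in a study that section 9.2 calls exploratory. This limits the weight of the point but does not make the test suit the design. The reservation in 9.2 concerns formal power calculations.

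A third is that every magnitude rests on assumed variances. This stands. The most extreme cell of the power table (0.1% against 99.8%) needs a correlation of 0.97 between a patient's two maps, and should not be read as the expected loss.

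A reader might also look for a level of variation in the catheter difference below which pooling points is safe. The documents do not support one. Any such threshold assumes independent points within a patient, and the sensitivity check shows the error exceeding 20% without that assumption.

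Finally, the test of means covers only part of the section 3 hypothesis, which also predicts a smaller low-voltage area. This point does not extend to that outcome.

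**Conclusion.** The concern holds. The named test does not fit a comparison in which the same patients supply both samples, and the unit of analysis is not stated. That mismatch follows from the text and needs no assumption.

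Its size does need assumptions. With patient means, the test is conservative and loses power when a patient's two maps are positively correlated, and the loss vanishes as that correlation approaches zero. With pooled points, type I error can far exceed 5% when the catheter difference varies between patients. It would be wrong to infer that the plan will certainly give false positives, or certainly miss a difference, because the direction depends on a unit the plan does not name.

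It would also be wrong to carry the point over to the main result. The primary outcome, the normal voltage range in controls, does not use this test. This should be corrected before analysis, but it does not threaten the study.

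**What to change.** **In 9.1**, replace the independent-sample t-test with a paired analysis and state that the patient is the unit. Compute one HD grid minus ablation-catheter difference for each patient with both maps, and apply a paired (one-sample) t-test to these values. Report the mean difference with its 95% CI and the number of patients contributing. That number matters because 7.9 allows for procedures cut short, where "then any data collected up to that point will be analysed", so a patient may lack a complete second map.

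**In 9.3**, average the matched-point differences and the segment differences within each patient first, then analyse those patient values in the same way.

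**Before analysis**, state which comparison is the main one. The choice is the sponsor's: the whole-chamber mean is simple but sensitive to unequal point coverage between catheters, whereas the matched-point difference addresses location.

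**Separately, and minor:** 9.1 extends the comparison to AF, whereas section 4 specifies sinus rhythm, 7.7 and the procedures table in Appendix B describe the ablation-catheter map during pacing, and 9.3 refers to sinus rhythm or the baseline pacing cycle length. The Appendix A flow chart is not shown in the text reviewed, so this is only wording to reconcile.

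The cost is a wording change before analysis. Data collection, sample size and the point-matching step stay as they are.

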9.2. The Number of Participants

The total number of participants will be 35; 30 with AF and 5 controls. Previous studies have revealed the presence of low voltage areas (<0.5mV) in approximately 35% of patients with persistent AF undergoing catheter ablation,(7) and in the one previous prospective study of patients without low voltage areas, intermediate amplitude regions were observed in 43%.(9) Our hypothesis is that conduction properties, and thus electrogram morphology will become abnormal at shorter cycle length. A sample of 35 is consistent with previous mechanistic exploratory studies and should include enough patients with regions of voltage amplitude <1.1mV according to prior results outlined above and allow comparisons between each cycle length. As this is an exploratory study we are not evaluating a specific intervention, formal power calculations have limited usefulness.

The control group will consist of 5 patients with presumed normal atria. Although this is a small number, a high number of points will be collected to allow good distribution of results. By analysing the combined total electrogram recordings and excluding patients with any risk factors for abnormal atrial substrate then this sample should provide adequate estimation of normal values.

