4. OBJECTIVES AND OUTCOME MEASURES

Objectives	Outcome Measures	Timepoint(s) of evaluation of this outcome measure (if applicable)
Primary To define the normal range of voltage amplitude identified using the Abbott EnSite Advisor HD grid (SE) catheter and HD wave solution and response to pacing cycle lengths using a control group with normal	Mean and distribution of left atrial voltage amplitude across the whole chamber and by segments with lower limit of normal defined as the upper 95% value within the segment with the lowest mean amplitude at long pacing cycle length	During ablation procedure

left atria		
Secondary: To characterise the left atrial electrophysiological substrate using electroanatomical voltage and activation mapping using the Abbott EnSite Advisor HD grid (SE) catheter during pacing using a basic cycle length and a single closely coupled extra-stimulus in a cohort of patients undergoing catheter ablation for atrial fibrillation.	A change in electrogram morphology from normal to abnormal (defined as ≥3 deflections lasting ≥50ms) between long and short pacing cycle length in regions of low (<0.5mV), intermediate (0.5-lower limit of normal defined from control group) and normal (defined from control group results) voltage amplitude.	During ablation procedure
	Difference in single vector conduction velocity at long and short cycle lengths in regions of low, intermediate and normal voltage.	During ablation procedure
In a subgroup of 20 patients: To compare electroanatomic voltage mapping (EAVM) performed with a bipolar contact force guided ablation catheter to the Abbott HD grid using orthogonal wave analysis in sinus rhythm.	1. Difference in voltage amplitude by each method in sinus rhythm 2. Surface area and proportion of points of scar (<0.05mV), low voltage (0.05-0.4mV), intermediate voltage and normal voltage (voltage cut-offs defined from control group).	During ablation procedure
In a subgroup of 10 patients: Correlate findings of high density contact mapping with AF propagation patterns using the AcQMap combined imaging and electrophysiological mapping system.	Correlate electrogram amplitude and morphology with regions of uniform, irregular, slow or rotational activation patterns during AF.	During ablation procedure

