7.6. Study visit (control group)

As part of standard care, a 12 lead ECG will be performed for all patients following arrival on the day of their procedure.

Venous access, placement of electrophysiology catheters, and completion of diagnostic electrophysiology study will be undertaken in line with standard clinical care. Trans-septal puncture for left atrial access will be undertaken and anticoagulation will be administered in line with standard protocols. Prior to any ablation, left atrial electroanatomical voltage mapping (EAVM) using the Abbott Advisor HD Grid (SE) mapping catheter using the orthogonal wave setting (HD wave solution) will then be undertaken. This will be conducted during bipolar pacing from the mid point of the coronary sinus catheter at a cycle length of 800ms for 4 beats followed by a single extrastimulus with coupling interval of 300ms. Care must be taken to keep the catheter in each position to record all 5 cycles before moving to acquire new points aiming for a minimum of 300 points in total with full and equal covering of the atrial surface. Interpolation threshold should be set to 7mm with points filtered to within 5mm of the surface anatomy (interior and exterior projection). Initial map collection should be specified as a CFAE map set to collect points with the catheter stationary for 5 seconds.

Following completion of the EAVM, the procedure continues in line with standard clinical practice. If, for any reason the EAVM is not performed then the patient will be removed from the study. If mapping has commenced but is incomplete then the data will still be used.

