9.3. Analysis of Outcome Measures

Control group:

All electrogram samples will be analysed at baseline (long) cycle length and classified as normal or abnormal (see above definitions in section 4). The same sampling points will then be analysed at short cycle length and classified in the same way. The proportion of electrograms changing from normal to abnormal will be recorded as will the change in electrogram amplitude and duration.

The whole chamber mean, median and distribution of voltage amplitude at long cycle length will be analysed. This will also be done for each atrial segment. The segment with the lowest mean amplitude will be identified and the cut-off for the value representing the upper 95% of recordings in that segment calculated. This will be used as the value representing the lower limit of normal for subsequent study analyses.

All participants:

All electrogram samples will be analysed at baseline (long) cycle length and classified as normal or abnormal (see above definitions in section 4). The same sampling points will then be analysed at short cycle length and classified in the same way. The proportion of electrograms classified as normal and abnormal at each cycle length will be calculated for the full sample set and according to baseline electrogram amplitude (<0.5mV, 0.5-lower limit of normal, and >lower limit of normal)(lower limit of normal defined above from analysis of the control group).

For each participant, conduction velocities will be analysed in regions of different baseline electrogram amplitude at both long and short cycle length. This will be done using the Turbomap feature in Precision to create an activation map (specified as measuring on maximum negative dV/dt). Conduction velocity will be calculated as a mean of 5 measurements using the difference in activation times between 2 points in a straight line at set distance through the region of least isochronal crowding. This will be done in regions of low, intermediate and preserved voltage at long and short cycle length.

The outcome measures will be assessed in all patients in whom the study procedure was performed.

Voltage mapping subgroup:

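### The precision of the lower limit of normal rests largely on 5 controls, yet the plan argues adequacy from pooled electrograms and gives this part of the primary outcome no patient-level interval

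*Combined protocol and SAP*

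**What the plan says.** Section 4 makes the lower limit of normal part of the primary outcome measure. Section 9.3 finds the segment with the lowest mean amplitude at long cycle length, with "the cut-off for the value representing the upper 95% of recordings in that segment calculated". I read this as the pooled 5th percentile of that segment. Section 9.3 continues: "This will be used as the value representing the lower limit of normal for subsequent study analyses".

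Section 9.2 supports the 5 controls with two reasons: "a high number of points will be collected to allow good distribution of results", and "excluding patients with any risk factors for abnormal atrial substrate". It concludes that "this sample should provide adequate estimation of normal values". The same section calls the study exploratory.

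The limit then closes a bracket in Section 4: "intermediate (0.5-lower limit of normal defined from control group". Low is below 0.5 mV and normal is above the limit. Sections 9.1 to 9.3 contain no confidence interval, per-patient summary or sensitivity analysis for the limit, and no rule for a limit at or below 0.5 mV.

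Two provisions affect how much each control contributes. Section 7.6 says of control maps: "If mapping has commenced but is incomplete then the data will still be used". Section 7.9 says, of deviations forced by clinical necessity: "It may be required to recruit additional patients if this occurs depending on the extent to which data had been collected". Neither gives a weighting rule.

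**The concern.** A large count of electrograms is not a large sample of normal atria. Extra points shrink only the within-patient part of the error; the between-patient part is fixed by having 5 patients. Excluding patients with risk factors may reduce that part, but it does not make points within a patient independent, and it supplies no measure of uncertainty.

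The limit sets the border between intermediate and normal voltage for all AF patients at once, so an error in it is shared rather than averaged out. Section 3 hypothesises that intermediate regions respond differently from preserved ones, and that contrast depends on where the border falls. Section 3 also intends the results as pilot data for larger multi-centre studies, where a limit quoted without an interval could be taken as settled.

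**Working it through.** **Plan's own figures.** 30 + 5 = 35, which agrees. No power, standard deviation or precision target is given, so nothing further can be reproduced.

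**Inputs from the documents.** 5 controls (9.2); a target of at least 300 points per map (7.6); 6 atrial segments (listed in 9.3 for the voltage-mapping subgroup, assumed to apply to controls). Hence 300/6 = 50 points per control per segment, and 5 × 50 = 250 pooled points in the segment that sets the limit.

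**Assumptions, not in the documents.** Log-normal amplitudes; within-patient log-SD 0.6; six segments with equal medians; three settings for the between-patient and patient-by-segment log-SDs: low (0.1, 0.1), middle (0.2, 0.15), high (0.3, 0.2).

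**Step 1: what the points are worth.** The latent correlation is r = (between² + segment²)/(between² + segment² + 0.6²). For the middle setting, 0.0625/0.4225 = 0.148. From the bivariate normal, the ICC of the indicator for lying below the 5th percentile is [P(both below) − 0.05²]/(0.05 × 0.95). The design effect is 1 + (m − 1) × ICC, with m points per control in the segment.

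| Spread | r | ICC | Design effect, m = 50 | 250 points worth | Design effect, m = 200 | 1,000 points worth |
|---|---|---|---|---|---|---|
| Low | 0.053 | 0.013 | 1.62 | 154 | 3.52 | 284 |
| Middle | 0.148 | 0.040 | 2.97 | 84 | 8.98 | 111 |
| High | 0.265 | 0.083 | 5.06 | 49 | 17.5 | 57 |

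Four times the points helps clearly in the low setting and little in the high one.

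**Step 2: sampling range of the limit.** Simulation of 5 controls × 6 segments, taking the pooled 5th percentile in the segment with the lowest pooled mean (10,000 runs at 50 points, 6,000 at 200). The interval that ignores patients is the order-statistic 95% interval.

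| Spread | 95% range, true limit 1.1 mV | 95% range, median 2.0 mV (true limit) | Runs ≤0.5 mV, median 2.0 mV | Coverage ignoring patients, 50 / 200 points |
|---|---|---|---|---|
| Low | 0.87–1.26 | 0.57–0.84 (0.73) | 0.05% | 87% / 65% |
| Middle | 0.80–1.36 | 0.50–0.85 (0.69) | 2.6% | 76% / 49% |
| High | 0.72–1.50 | 0.41–0.87 (0.63) | 15.5% | 66% / 38% |

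With zero between-patient spread the same code gives 96% and 95% coverage, so the shortfall comes from clustering. At a true limit of 1.1 mV, none of 10,000 runs in any setting fell to 0.5 mV or below. At median 2.0 mV, with one clearly lowest segment instead of equal medians, the 2.6% and 15.5% become 1.3% and 8.1%.

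**Step 3: effect on the brackets.** Assume AF amplitudes are log-normal, median 2.0 mV, log-SD 0.8, and the true limit is 1.1 mV. The intermediate share is F(limit) − F(0.5): 18.6% at 1.1 mV, 8.6% to 27.4% at the ends of the middle range, 6.0% to 31.7% at the ends of the high range. Suppose 30% of points between 0.5 and 1.1 mV change morphology and 5% above. The true contrast is 25 percentage points. At a limit of 1.497 mV the intermediate bracket gives (18.6 × 0.30 + 13.1 × 0.05)/31.7 = 19.7%, a contrast of 14.7. At 0.721 mV the contrast is 21.5. Across the middle and high ranges it is about 15 to 22.

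**Step 4: an interval that respects patients.** A leave-one-control-out jackknife on the log scale (t with 4 df, segment fixed as chosen from all five) covered about 90% to 94%; a cluster percentile bootstrap covered about 83% to 84%. The median jackknife half-width is a factor of 1.28, 1.38 and 1.51 in the three settings.

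**Step 5: weighting.** As an illustration, one map of 100 points beside four of 300 gives that control 100/1,300 = 8% of the points instead of 20%.

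**The case against.** The strongest reply is that the study is declared exploratory, that 9.2 itself says 5 is few, and that the long control-only exclusion list in 6.3 plausibly makes the controls alike. This partly stands. It excuses the missing power calculation, and in the low-spread setting the design effect is only 1.6 and more points do help. It does not support a claim of adequacy for a primary estimate that has no precision statement, and even in that setting an interval ignoring patients covers 87%.

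All spreads are assumed. That is true, so the size is uncertain. The direction holds whenever controls differ from one another.

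A reader might infer that a wrong limit invalidates the AF tests. The documents do not support that. The chi-square test in 9.1 compares cycle lengths within a bracket, and brackets are set on baseline amplitude, so a misplaced limit relabels the same points at both cycle lengths. It changes which tissue the test describes and does not bias the comparison.

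A reader might also infer that the intermediate bracket is likely to vanish. That is not supported either. The only anchors in the documents are 1.1 and 1.3 mV from other technology (Section 3), and Section 3 expects higher amplitudes from the HD grid than from bipolar mapping. Collapse remains possible, because Section 3 also says that cut-offs vary by catheter and are not established for this one.

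Unequal weighting is a possibility only: 7.6 aims for at least 300 points with full, even coverage.

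**Conclusion.** The point holds and should be fixed. The adequacy argument treats electrograms as the sample when patients largely determine precision, and a primary-outcome quantity is carried forward as a constant without an interval. Under the assumed spreads, 250 points are worth about 49 to 154, and the limit's 95% sampling range runs from about 0.79–1.15 times the true value (low spread) to 0.65–1.37 times (high spread).

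The downstream effect is moderate: in the illustration the intermediate-versus-preserved contrast shrinks but does not reverse. The missing rule for a limit at or below 0.5 mV is a real but secondary gap. It bites only if the true limit for this catheter is well below 1.1 mV. Confidence is medium, because every magnitude rests on assumed spreads and medians.

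**What to change.** 1. In 9.2, replace the adequacy statement with: *the lower limit of normal is a pilot estimate from 5 patients, and between-patient variation limits its precision.*
2. In 9.3, report the limit with an interval that treats patient as the cluster, for example the jackknife in Step 4, stated to be rough with 5 clusters. List the five leave-one-out values. Give each control equal weight, at least as a sensitivity analysis, because incomplete maps are kept.
3. Repeat the bracketed morphology proportions and the voltage-area outcomes at both ends of that interval. Leave out conduction velocity: its regions would have to be redrawn and velocities re-measured, up to 30 patients × 2 regions × 2 cycle lengths × 5 measurements × 2 limits = 1,200 extra measurements.
4. Before AF data are bracketed, fix the analysis to be used if the point estimate is at or below 0.5 mV, for example baseline amplitude as a continuous variable for morphology. If only the lower end of the interval reaches 0.5 mV, keep the three brackets and add that analysis as a sensitivity analysis. Switching on the lower end would fire too often: in about 59% and 78% of runs (middle and high spread, median 2.0 mV), when the limit itself is that low in only about 3% and 15%.
5. As a separate definitional point, reconcile low voltage below 0.5 mV (Section 3 hypothesis) with 0.05–0.4 mV (Section 4, voltage-mapping subgroup), and state where intermediate starts there.

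The cost is wording in 4, 9.2 and 9.3 and a few extra analysis runs, with no new patients or procedures. The downside is a visibly wide interval, about ×/÷ 1.3 to 1.5 under the assumptions.
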